7.3 Clinical Laboratory Assessments

Measurement of clinical laboratory parameters will be conducted at the time points presented in the [Appendix B](#). For purposes of analyses, laboratory results based upon standardized units will be used.

Results from all clinical laboratory parameters including pregnancy test will be presented in data

listings for the FAS.

For the IAS, a summary of the laboratory parameters at baseline, each scheduled post-baseline visit and change from baseline will be provided by test category (e.g., chemistry, hematology, etc.). Continuous clinical laboratory values will be summarized by presenting descriptive statistics. UACR will be considered as a categorical variable with three categories: <30 mg/g, 30 – 299 mg/g, and \geq 300mg/g. Qualitative results at each time point measured will be summarized by presenting the number and percentage of subjects.

Laboratory assessment results from unscheduled visits will be excluded from table summaries but will be included in data listings. When there are repeat measurements for a given visit (i.e. retests), only the last measurement will be listed and used in the table summaries.

Results that are reported as above or below the limit of quantitation (e.g. <4, >10) will be not be imputed and will be treated as missing values for summarization purposes. The originally reported result (e.g. <4, >10) will be displayed in the listings.

Laboratory abnormalities will be defined using the NCI CTCAE grading scheme. Abnormal laboratory values will be flagged as above or below the normal range.

For the IAS, the incidence of treatment-emergent laboratory abnormalities, defined as values that increase at least one toxicity grade between baseline and post-baseline up to six months following REACT injection, will be summarized. If baseline and pre-injection data are missing, then any graded abnormality (i.e., at least a Grade 1) will be considered as treatment-emergent. These values will be summarized descriptively for the IAS.

Additionally, for the IAS, shift tables (shift from baseline to the worst post-baseline value) will be presented split by the inter-injection, post-second injection period, and the post-injection period as described in [section 4.9](#). Shift tables will describe the shift in CTCAE grades when available, or the shift from low/normal/high when CTCAE grades are not available.

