## 9.7. Safety Analysis

### 9.7.1. Laboratory Evaluations

Baseline values will be collected immediately prior to REACT injection. Observed and change from baseline laboratory data will be summarized via sample size, mean, standard deviation, median, minimum, and maximum for the continuous variables as well as frequency and proportion for the categorical variables. Laboratory abnormalities will be defined using the NCI CTCAE grading scheme. Abnormal laboratory values will be flagged as above or below the normal range. The results of laboratory testing for renal function, specifically sCr, BUN, and urinary albumin, are of particular interest for this study.

The incidence of treatment-emergent laboratory abnormalities, defined as values that increase at least one toxicity grade between baseline and any time post-baseline up to six months following REACT injection, will be summarized. If baseline data are missing, then the latest value between

biopsy and injection will be used as the baseline value. If baseline and pre-injection data are missing, then any graded abnormality (i.e., at least a Grade 1) will be considered as treatment-emergent. These values will be summarized for both the full analysis set and the injection analysis set. Observed and change from baseline values will be presented as descriptive statistics; generating inferential statistics is not planned. These data will be provided in a tabular listing.

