7.4 Vital Signs

Vital signs are taken throughout the procedure during biopsy and first/second REACT injections. As peri-procedure vital signs will be impacted by the procedure (e.g., sedation), the baseline value for all vital signs will be defined as the last non-missing value taken on a date *prior* to the date of first REACT injection. Diastolic and systolic blood pressure measurements are taken in triplicate at the pre-biopsy visit (Day -3 to Day -1), and the pre-injection visit (Day -14 to -10). The average of the blood pressure measurements will be used analysis purposes. For example, in most cases, the baseline blood pressure will come from the pre-injection visit (Day -14 to -10). In those cases, the baseline will be set to the average of the measurements taken for that visit.

Descriptive summaries of the vital signs (both raw and change from baseline values) including systolic and diastolic blood pressure, heart rate, respiratory rate, body temperature, weight and BMI will be prepared by visit using the IAS. A listing of all the vital sign measures will also be provided for the FAS.

Vital sign results from unscheduled visits will be excluded from table summaries but will be included in data listings. Additionally, measures taken during procedures will not be summarized, only listed.

If there is a difference between the IAS and FAS, then summaries conducted using the IAS will

be repeated using the FAS.

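### SAP 7.3 does not exempt its worst-value shift tables and its treatment-emergent laboratory table from the unscheduled-visit and last-retest rules, so both can understate laboratory toxicity

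*SAP*

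**What the plan says.** SAP 7.3 starts with by-visit tables: "a summary of the laboratory parameters at baseline, each scheduled post-baseline visit and change from baseline". Rules on which records count come next:

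- Unscheduled visits: "Laboratory assessment results from unscheduled visits will be excluded from table summaries but will be included in data listings".
- Retests at a visit: "only the last measurement will be listed and used in the table summaries".
- Results beyond a quantitation limit are not imputed and "will be treated as missing values for summarization purposes".

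The section then introduces CTCAE grading and two further kinds of display, both on the injection analysis set:

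- Treatment-emergent abnormalities, defined as "values that increase at least one toxicity grade between baseline and post-baseline up to six months following REACT injection".
- "shift tables (shift from baseline to the worst post-baseline value", closing bracket omitted here), split into the inter-injection, post-second injection and post-injection periods. They use CTCAE grades where these exist and low/normal/high otherwise.

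The SAP does not say which records feed these displays. Protocol 9.7.1 defines the treatment-emergent abnormality as "values that increase at least one toxicity grade between baseline and any time post-baseline up to six months following REACT injection".

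**The concern.** The record-selection rules are worded for table summaries in general. A programmer who follows them would build the shift and treatment-emergent tables from scheduled results only, taking the last value wherever a retest exists. Under Protocol 8.1.1, unscheduled visits are held to assess and follow up adverse events, so they are a plausible place for a peak abnormality. A retest is likewise a plausible place for an abnormal first value to be replaced.

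At stake is the reading of the laboratory toxicity tables in a trial whose primary objective is safety. Someone looking at a table of worst values will assume that it contains the worst recorded value. A superseded retest is the sharper case, because the rule removes it from the listings as well. Yet 7.3 also says that results from all laboratory parameters will be listed.

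**Working it through.** The plan gives no figure to reproduce. The check applies the rules to records and then sizes one omission.

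**Inputs.** Up to 10 subjects (SAP 9; Protocol 9.1). Both displays use the injection analysis set, that is, subjects with at least one injection (SAP 4.2, 7.3). Periods are from SAP 4.9. Treatment-emergent means a rise of at least one grade over baseline (SAP 7.3; Protocol 9.7.1). The grades below are invented to test the logic, with baseline grade 1 throughout.

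**Step 1: apply the two rules.**

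| Post-baseline results | Worst, all results | Worst, rules as written | Treatment-emergent, all results | Treatment-emergent, as written |
|---|---|---|---|---|
| Scheduled 1, unscheduled 3, scheduled 1 | 3 | 1 | yes | no |
| Scheduled 3 with retest 1, then scheduled 1 | 3 | 1 | yes | no |
| Scheduled 1 with retest 3 | 3 | 3 | yes | yes |
| Scheduled 2, unscheduled 3 | 3 | 2 | yes | yes |

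Rows 1 and 2 lose the subject from both displays. Row 3 shows that the retest rule does no harm when the later value is the worse one. Row 4 shows the limit of the point: the shift table is wrong, but the treatment-emergent count is not.

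**Step 2: direction.** With baseline held fixed, the highest grade in a subset of results cannot exceed the highest grade in the full set. The error can only understate the worst grade, and it can only remove subjects from the treatment-emergent count.

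**Step 3: size of one omission.** One subject wrongly left out changes the treatment-emergent incidence by 1/n:

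- n = 10: 1/10 = 10 points. As an illustration, the exact 95% interval goes from 0 to 30.8% (0/10) to 0.3 to 44.5% (1/10).
- n = 8 (assumed): 1/8 = 12.5 points.
- n = 5 (assumed): 1/5 = 20 points.

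**Step 4: displays touched.** There are 3 shift tables + 1 treatment-emergent table = 4. A post-baseline value belongs to one of the inter-injection and post-second injection periods (1 table) and to the post-injection period (1 table). If it lies in the six-month window it also belongs to the treatment-emergent table (0 or 1). One dropped value can therefore affect at most 2 or 3 of the 4.

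**Step 5: look for an exception elsewhere.** SAP 4.4 (windows), 4.5 (missing data), 4.7 (baseline) and 10 (differences from the protocol) contain none. Where the SAP wants unscheduled visits used, it says so: the eGFR slope model in 6.3.4. Where it wants the most severe episode counted, it says so: the AE tables in 7.2.5.

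**Step 6: frequency.** The documents give no rate of unscheduled draws or of retests, so the expected number of missed subjects cannot be derived.

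**The case against.** The best counter-argument is that the rules were meant for by-visit summaries only. They come directly after the by-visit paragraph and before grading is introduced. A near-identical sentence appears in SAP 7.4, where the tables are by visit ("Vital sign results from unscheduled visits will be excluded from table summaries but will be included in data listings"), and again in 7.5. The shift tables cover continuous periods, and asking for the worst value is itself a specific instruction. The protocol counts a rise at any time, and SAP 10 declares no departure from that. This reading is plausible and may be what was intended. It is not stated, however, and it does not rescue the superseded retest, because that rule governs listings as well as tables.

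The backstops are real. Unscheduled results stay in the listings, which can be read subject by subject in a trial of this size. The AE definition in Protocol 8.1.1 includes abnormal laboratory findings, and Protocol 8.3 has AEs documented through laboratory reports recorded. But 8.3 also says that a clinically significant laboratory change need not be reported as an AE unless it is an SAE or leads to discontinuation of treatment or withdrawal. The AE tables are therefore only a partial backstop.

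A reader might infer three stronger things that the documents do not support:

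- That every missed worst grade moves an incidence by at least 10 points. The treatment-emergent table counts any one-grade rise, so a subject with another retained rise in the window is still counted (row 4 of the working).
- That the beyond-limit rule also removes graded results. Summarization may not extend to grading, and no assay limits are given, so no analyte is shown to be affected.
- That the SAP dropped the words *any time* in order to narrow the protocol definition. The remaining words cover the same interval, and nothing shows such an intention.

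**Conclusion.** The point holds in a limited form. As written, SAP 7.3 allows a shift table to miss a subject's worst value. It also allows the treatment-emergent table to miss a subject whose only qualifying rise was unscheduled or superseded by a retest. The error runs in one direction, towards less apparent toxicity, and it sits poorly with Protocol 9.7.1.

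Each subject wrongly omitted from the treatment-emergent count costs 10 points at the planned maximum of 10, and more if fewer are treated. Whether any subject would be omitted is unknown. This conclusion assumes that the rules are applied literally; under the by-visit reading only the unlisted retest remains. The primary endpoint of procedure- or product-related AEs is not touched, and no hypothesis test is planned. The change is worth making because the trial is about safety and the correction is cheap.

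**What to change.** In SAP 7.3:

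- State that the unscheduled-visit and last-retest rules apply to by-visit summaries only.
- For the shift and treatment-emergent tables, use all valid post-baseline results within each table's own period: scheduled, unscheduled and every repeat. Leave out only results documented as invalid.
- List every repeat measurement.
- As a minor clarification, say whether a beyond-limit result is graded when its reported bound settles the CTCAE grade or the low/normal/high category. This substitutes no value and so stays consistent with SAP 4.5.

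The cost is a few sentences and some programming, with no new data. The downside is somewhat higher counts of abnormal values, some of them transient. If the by-visit reading was always intended, the change to the tables only writes that down.

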2.2.2 Secondary Endpoints

Renal-specific laboratory assessments through 24 months post last injection. Renal-specific laboratory assessments include: eGFR as estimated by three Chronic Kidney Disease Epidemiology Collaboration (CKD-EPI) equations [2009 CKD-EPI serum creatinine equation^[1], 2012 CKD-EPI cystatin C equation^[2], and 2012 CKD-EPI serum creatinine-cystatin C equation^[3]], random urine albumin to creatinine ratio (UACR), 24 hour urine albumin, 24 hour urine protein, cystatin C, serum creatinine, blood urea nitrogen, bicarbonate, potassium, phosphorus, calcium, intact parathyroid hormone (iPTH), hemoglobin, and hematocrit.

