3. INVESTIGATIONAL PLAN

3.1 Study Design

This is a multi-center, prospective, open-label, single-group study. Up to 10 subjects who complete screening procedures and satisfy all inclusion and exclusion criteria specified in the protocol will be enrolled into the study immediately prior to the biopsy. All subjects will be treated with two REACT injections 6 months (+4 weeks) apart after biopsy. Subjects will be followed over a 24 month period post the last injection. See Appendices A-B for the Schedule of Events.

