3.2.3 Dosing Schedule

The dose of REACT will be 3×10^6 cells/g estimated kidney weight and the dosing volume will be 3.0 mL for each 100 g of kidney weight. It is anticipated that all subjects will receive two planned REACT injections to allow dose-finding and evaluate the duration of effects. The series of 2 REACT injections will be administered 6 months apart with a study visit window of 4 weeks.

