4.7 Baseline Definition

Unless otherwise specified, baseline is defined as the last non-missing value prior to the first REACT injection.

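### The treatment-emergent laboratory incidence table stops six months after an unnamed injection and omits at least 18 of the 30 to 31 planned months; other laboratory outputs do cover them

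*SAP*

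**What the plan says.** **The window.** SAP Section 7.3 will summarise, for the injection analysis set, the incidence of treatment-emergent laboratory abnormalities, meaning "values that increase at least one toxicity grade between baseline and post-baseline up to six months following REACT injection". Protocol Section 9.7.1 sets the same limit: "baseline and any time post-baseline up to six months following REACT injection, will be summarized". Neither names the injection. SAP Section 10, which lists differences from the protocol, does not discuss the limit.

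**The baseline.** Under SAP Section 4.7, "baseline is defined as the last non-missing value prior to the first REACT injection". Section 7.3 sets no other baseline for laboratory data.

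**The schedule.** SAP Section 3.1 states: "All subjects will be treated with two REACT injections 6 months (+4 weeks) apart after biopsy". It adds: "Subjects will be followed over a 24 month period post the last injection". SAP Section 3.2.3 gives the four weeks without a sign: "The series of 2 REACT injections will be administered 6 months apart with a study visit window of 4 weeks".

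**The horizon elsewhere.** SAP Section 2.1 sets the study objectives over the 24 months after the last injection. The secondary endpoint in SAP Section 2.2.2 is "Renal-specific laboratory assessments through 24 months post last injection". Protocol Table 2 schedules laboratory visits to Month 24 after the last injection. Treatment-emergent adverse events (SAP Section 7.2.1) have no six-month limit.

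**Other laboratory outputs.** SAP Section 7.3 also plans listings, by-visit summaries with change from baseline, and shift tables from baseline to worst post-baseline value. The shift tables use CTCAE grades where these exist and are split into the inter-injection, post-second-injection and post-injection periods. Under SAP Section 4.9 the last two periods run to withdrawal or completion.

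**The concern.** The laboratory table that carries the treatment-emergent label covers a much shorter time than the objective, the laboratory endpoint, the sampling schedule and the adverse-event tables. Its starting point is also left open. A subject whose potassium or hemoglobin first worsens by a grade at Month 9 or Month 12 after the second injection would not be counted in it under any reading. If the clock starts at the first injection, a study of a two-injection regimen would take this figure from one injection.

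The consequences are limited but real:

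- Two tables built from the same data could give different numbers of worsening subjects for the same analyte, with no stated reason.
- Treatment-emergent would mean one period for adverse events and another for laboratory values.
- The adverse-event tables cannot be relied on to fill the gap. Protocol Section 8.1.1 includes abnormal laboratory findings in the definition of an adverse event. Section 8.3, however, does not require even a clinically significant laboratory change to be reported as one unless it is serious or leads to discontinuation or withdrawal.
- With up to 10 subjects, each subject left out moves an incidence by at least 1/10, or 10 percentage points.

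**Working it through.** **Inputs.** Window: 6 months (SAP 7.3, Protocol 9.7.1). Interval between injections: 6 months, plus up to 4 weeks (SAP 3.1). Follow-up after the last injection: 24 months (SAP 3.1). Laboratory visits after the last injection: Days 1, 14 and 28 and Months 2, 3, 6, 9, 12, 15, 18, 21 and 24, which is 12 visits (Protocol Table 2). One month is taken as 365.25/12 = 30.44 days, so 4 weeks = 28/30.44 = 0.92 month.

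**The plan's own figure.** Protocol Section 4.5 gives a study duration of 31 months: 1 month before the first injection + 6 + 24 = 31. This reproduces.

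**Planned time after the first injection.** Interval + 24: from 6.0 + 24 = 30.0 to 6.92 + 24 = 30.92 months.

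**Coverage under each reading.** Missed = total − covered. The first figure is for a second injection at 6.0 months, the second for 6.92 months.

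| Six months counted from | Covered (months) | Missed (months) | Share missed |
|---|---|---|---|
| First injection | 6 | 24.0 to 24.92 | 24/30 = 80% to 24.92/30.92 = 81% |
| Each injection separately | 6 + 6 = 12 | 18.0 to 18.92 | 18/30 = 60% to 18.92/30.92 = 61% |
| Last injection, counting continuously from the first | 12.0 to 12.92 | 18.0 | 18/30 = 60% to 18/30.92 = 58% |

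The minimum is 24 − 6 = 18 months. A subject who receives only one injection has 24 planned months, of which 18 are missed (75%).

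**Visits.** With the first injection as anchor, the window closes at 6 months. The second injection falls at 6.0 to 6.92 months, so all 12 later laboratory visits are outside. On the other two readings the six visits from Month 9 to Month 24 are outside. The Month 6 visit has a window of ±7 days, so a visit a few days late could also miss a strict cut.

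**Sensitivity to the unsigned window.** If the 4 weeks could also run the other way, the second injection could come at 6 − 0.92 = 5.08 months, and the total would be 29.08 months. The first-injection reading would then include 0.92 month after the second injection and miss 23.08 of 29.08 months (79%). The other readings would still miss 18 months (62%). This is why the first-injection reading is said to contain essentially nothing, rather than strictly nothing, after the second injection.

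**Comparison with the shift tables.** Whether a subject ever rose by at least one grade in a period depends only on the baseline grade and the worst grade in that period. For CTCAE-graded tests with a baseline value, the cells above the diagonal of the shift table give that count. On the same values, a six-month count can equal the full-period count or fall below it, but cannot exceed it.

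**The case against.** The strongest reply is that most of what is wanted is already planned. The shift tables span the same three periods to study end and let a reader rebuild the full-horizon count for graded tests. The secondary laboratory endpoint is analysed separately in SAP Section 6.2 at each time point with no six-month cut; only values after the start of dialysis are dropped. Listings for at most 10 subjects can be read in full. All of this stands. A reader might infer that late laboratory toxicity goes unreported or that an endpoint is truncated. The documents do not support either inference.

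A reader might also infer that the anchor must be the first injection, so that everything after the second is lost. The text permits this, and the baseline favours it, but it is not stated. The SAP writes of the first injection explicitly when it means it (Sections 4.3, 4.7 and 6.3.5). In Sections 6.3.1 to 6.3.3 it uses the unqualified term for time points not limited to the first. Protocol Section 7.2.4 records all medications for about six months after each injection, so an after-each reading is plausible too.

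Finally, a short window may be defensible in subjects entering with an eGFR of 14 to 20, because it limits how much natural progression is counted as treatment-emergent. That is a fair reason to keep a six-month figure. It does not justify leaving the anchor unnamed, or making that figure the only incidence, when adverse events carry no such limit.

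**Conclusion.** The point holds for the treatment-emergent laboratory incidence table and no further. Followed as written, the table omits at least 18 of the planned 30 to 31 months after the first injection under every reading (58% to 61%, or about 80% with the first injection as anchor). It cannot give a higher count than the shift tables for the same graded tests, and it conflicts with the period used for adverse events.

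This rests on complete planned follow-up; a subject who leaves early loses less. The 18-month minimum depends neither on which injection is meant nor on the sign of the 4-week window. The loss of essentially all time after the second injection depends on the first-injection reading. No hypothesis test is planned, so no error rate or power is affected. This should be corrected, but it does not threaten the study's primary endpoint.

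**What to change.** In SAP Section 7.3:

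1. Define a treatment-emergent laboratory abnormality as a rise of at least one CTCAE grade from baseline at any time from the first injection to end of study. Keep the existing rule for missing baseline and pre-injection data.
2. Tabulate it by the inter-injection, post-second-injection and post-injection periods of SAP Section 4.9, consistent with the shift tables.
3. Keep the six-month limit as an additional row, with the anchor named: six months after the first injection and, separately, six months after the second.
4. List the change from Protocol Section 9.7.1 in SAP Section 10.

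The wording on the interval between injections (signed in SAP Section 3.1, unsigned in Section 3.2.3) should be reconciled so that the periods are unambiguous.

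The new window would cover all 30.0 to 30.92 planned months. That adds 18 months if the current anchor is the last injection and 24.0 to 24.92 months if it is the first. The cost is SAP wording and programming, since the data are already collected. The drawback is a higher incidence, because natural progression of kidney disease over the follow-up is included. The split by period and the six-month rows let a reader separate early from late changes.
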